4.2.2.2 Restrictions on diet and life style

Moisturizers/emollients containing retinoids and the use of tanning beds are not allowed during the trial.

4.2.2.3 Restrictions regarding women of childbearing potential

A serum beta-human Chorionic Gonadotropin (β -hCG) test will be performed at screening in women of childbearing potential. A local urine pregnancy test will be then performed as indicated in the Flow Chart. Any woman with a confirmed positive pregnancy test during screening is not eligible for the trial. A positive urine pregnancy test during the treatment periods of the trial requires immediate interruption of trial treatment until serum β -hCG is performed and found to be negative. If the serum β-hCG test is positive, the patient must be discontinued from treatment.

Women of childbearing potential must use the contraception methods described in the patient information for 6 months after the last dose of trial drug. Acceptable methods of birth control include, for example, birth control pills, intrauterine devices (IUDs), surgical sterilization, vasectomized partner.

Women of childbearing potential are defined as:

- Having experienced menarche and
- Not postmenopausal (12 months with no menses without an alternative medical cause) and
- Not permanently sterilized (e.g., tubal occlusion, hysterectomy, bilateral oophorectomy or bilateral salpingectomy).
- Women must not breast-feed for at least six months after the last adalimumab treatment.

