3.3.2 Inclusion criteria

- 1. Males and females aged ≥ 18 to < 80 years at screening who have a diagnosis of moderate-to-severe chronic plaque psoriasis (with or without psoriatic arthritis) for at least 6 months before the first administration of trial drug (a self-reported diagnosis confirmed by the Investigator is acceptable), and which has been stable per Investigator opinion for the last 2 months with no changes in morphology or significant flares at both screening and baseline:
 - a. involved body surface area (BSA) $\geq 10\%$ and
 - b. PASI score ≥ 12 and
 - c. sPGA score of ≥ 3 .
- 2. Participants of reproductive potential (childbearing potential²) must be willing and able to use highly effective methods of birth control per International Council for Harmonisation (ICH) M3 (R2) that result in a low failure rate of less than 1% per year when used consistently and correctly during the trial and for 6 months following completion or discontinuation from the trial medication. A list of contraception methods meeting these criteria is provided in the Section 4.2.2.3 and patient information.
- 3. Signed and dated written informed consent in accordance with Good Clinical Practice (GCP) and local legislation prior to admission to the trial.
- 4. Patients who are candidates for systemic therapy or phototherapy according to Investigator judgement.

² A woman is considered of childbearing potential (WOCBP), i.e. fertile, following menarche and until becoming postmenopausal unless permanently sterile.

Permanent sterilisation methods include hysterectomy, bilateral salpingectomy and bilateral oophorectomy. Tubal ligation is NOT a method of permanent sterilisation.

A postmenopausal state is defined as no menses for 12 months without an alternative medical cause.

Page 27 of 105

Proprietary confidential information © 2019 Boehringer Ingelheim International GmbH or one or more of its affiliated companies

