5.2 ASSESSMENT OF SAFETY

At the Screening Visit, the medical examination will include documentation of patient information, informed consent, demographics including height and body weight, smoking and alcohol history, relevant medical history and concomitant therapy, review of inclusion and exclusion criteria, review of vital signs (blood pressure, pulse rate, temperature), 12-lead ECG, laboratory tests (including virus screening, IGRA/PPD test [where applicable], pregnancy test for females), and a physical examination.

On other visits, it will include review of vital signs, 12-lead ECG, laboratory tests, pregnancy test for females and a physical examination.

Adverse events and concomitant therapies will be assessed throughout the trial.

Whenever possible, the same person should perform the physical examination throughout the trial (i.e., for all patients at each trial site).

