5.2.3 Safety laboratory parameters

The laboratory tests listed in Table 5.2.3: 1 will be analysed by a central laboratory. The central laboratory provider will also provide the materials for blood sampling. Instructions for the labelling, storage, and shipment of the samples as well as details of all blood variable units and reference ranges can be found in the Laboratory Manual.

Pregnancy testing will be performed by a central laboratory using serum at screening and local laboratory using urine at all applicable visits thereafter.

For time points of laboratory sampling, see the Flow Chart.

Laboratory results (i.e., all safety laboratory and clinical laboratory data relevant for current clinical practice) of the patients will be available to the respective Investigator (via laboratory reports) and to the sponsor (via the central laboratory website) and selected abnormal laboratory alerts will be flagged to the site and sent to sponsor in real time.

The Investigator must assess all laboratory results, evaluate any change in laboratory values, and review all clinical laboratory tests for potential clinical significance at all time points throughout the trial. The Investigator should endeavor to provide a reason for all out-of-range results deemed not clinically significant. If the Investigator determines a laboratory abnormality to be clinically significant, it will be considered an AE / SAE (see Section 5.2.6.1); however, if the laboratory value abnormality is consistent with a current diagnosis, it will be documented accordingly.

Table 5.2.3: 1 Laboratory tests

Category	Test name
Haematology	Het
	Hb
	RBC count / erythrocytes
	White blood cells / leukocytes
	Platelet count / thrombocytes
Diff. Automatic	Neutrophils (relative count)
	Lymphocytes (relative count)
Diff. Manual (if Diff Automatic is abnormal)	Neutrophils, bands (stabs)
	Neutrophils, polymorphonuclear
	Lymphocytes
Enzymes	AST (GOT)
	ALT (GPT)
	Creatine Kinase (CK)
	CK-MB, only if CK is elevated
	Gamma-Glutamyl Transferase (GGT)
Electrolytes	Calcium
	Sodium
	Potassium
	Chloride
Substrates	Glucose
	Creatinine
	Bilirubin total
	Bilirubin direct (if total is elevated)
	Bilirubin indirect (if total is elevated)

Page 43 of 105

Proprietary confidential information © 2019 Boehringer Ingelheim International GmbH or one or more of its affiliated companies

	Total protein Albumin
II. B	Cholesterol, total
Urine Pregnancy test (only for female patients of	Human Chorionic Gonadotropin in the urine

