childbearing potential) at randomization and	
continued as indicated in the Flow Chart (including	
EoT)	H C Cl : C I : C
Serum Pregnancy test (only for female patients of	Human Serum Chorionic Gonadotropin
childbearing potential) at screening and if urine	
pregnancy test is positive)	
Urinalysis (dipstick)	Urine Protein
	Urine Glucose
	Urine RBC / erythrocytes
Screening for infections (only at screening)	Hepatitis B (HBsAg, anti-HBc)
	Hepatitis C (anti-HCV)
	HIV-1 and HIV-2 antibody (qualitative, where
	mandated by local authorities, at the discretion of the
	Investigator where clinically indicated)
Screening for infections (at screening, Visit 14, EOT,	TB test (IGRA: QuantiFERON® Gold
and optional retest at Unscheduled visit)	assay/T-SPOT®.TB)
	(PPD skin test at the discretion of the Investigator
	where clinically indicated) ¹

Abbreviations: ALT=alanine aminotransferase; AST=aspartate aminotransferase; CK-MB=creatine kinase-MB; EoT=End-of-Treatment; GGT=gamma-glutamyl transferase; GOT=glutamic-oxaloacetic transaminase; GPT=glutamic pyruvic transaminase; Hb=hemoglobin; HBsAg= hepatitis B surface antigen; Hct=hematocrit; HIV=human immunodeficiency virus; IGRA=interferon gamma-release assay; PPD=purified protein derivative; RBC=red blood cell; TB=tuberculosis

1 There is the trial site option to perform a PPD skin test, although this will not be provided or performed at Central Lab.

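### Two definitions of childbearing potential disagree on tubal ligation, so the specific testing rules require up to 8 pregnancy tests or none for the same woman

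*Protocol*

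**What the plan says.** Protocol Section 3.3.2, footnote 2, attached to inclusion criterion 2, treats a woman as of childbearing potential from menarche to menopause unless she is permanently sterile. It names hysterectomy, bilateral salpingectomy and bilateral oophorectomy as permanent methods and adds: "Tubal ligation is NOT a method of permanent sterilisation".

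Section 4.2.2.3 defines the same term again in a bullet list. The sterilisation bullet reads: "Not permanently sterilized (e.g., tubal occlusion, hysterectomy, bilateral oophorectomy or bilateral salpingectomy".

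The term controls testing in three places:

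- **Flow Chart:** the pregnancy-test row is restricted to women of childbearing potential.
- **Section 4.2.2.3:** the screening serum test is for these women, with urine tests afterwards at the Flow Chart visits.
- **Table 5.2.3: 1:** both entries carry the restriction. They begin "Urine Pregnancy test (only for female patients of" and "Serum Pregnancy test (only for female patients of", and each continues with childbearing potential.

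Section 5.2.3 gives the method: "Pregnancy testing will be performed by a central laboratory using serum at screening and local laboratory using urine at all applicable visits thereafter". Section 4.2.2.3 gives the consequence of a positive result: "A positive urine pregnancy test during the treatment periods of the trial requires immediate interruption of trial treatment". Discontinuation follows if the serum test is also positive.

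Section 5.2 is less specific and omits the restriction: "On other visits, it will include review of vital signs, 12-lead ECG, laboratory tests, pregnancy test for females and a physical examination".

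**The concern.** One term has two definitions in current text, and they give opposite answers for an identifiable group: premenopausal women with ligated tubes and no hysterectomy, bilateral salpingectomy or bilateral oophorectomy. Neither definition refers to the other for its meaning, and neither amendment description addresses the point. About 80 sites are planned. Two of them could handle identical patients differently, and each could cite the Protocol.

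At stake is who is pregnancy-tested while on study drug, and therefore who can trigger the interruption and discontinuation rule. This is a site-conduct rule that belongs in the Protocol; an analysis plan would not settle it. It does not affect the primary endpoints, sample size or error control. Nor is a gap in participants' contraception alleged, because Section 4.2.2.3 accepts surgical sterilisation: "Acceptable methods of birth control include, for example, birth control pills, intrauterine devices (IUDs), surgical sterilization, vasectomized partner".

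**Working it through.** **Step 1. Apply each definition to the same woman** (premenopausal, tubal ligation only).

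| | Footnote 2, Section 3.3.2 | Section 4.2.2.3 |
|---|---|---|
| Past menarche, not postmenopausal | yes | yes |
| Ligation or occlusion counts as permanent sterilisation | no, stated outright | yes, given as an example |
| Of childbearing potential | **yes** | **no** |

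The step from ligation to occlusion is a medical inference: ligation is one way of occluding the tubes. The Protocol defines neither word.

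**Step 2. Count the scheduled tests if she is of childbearing potential.** The Protocol prints no total, so the marks in the two Flow Chart pregnancy-test rows are counted by column.

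- Screening to Week 24: Visits 1, 2, 6, 9 and 13 (screening, baseline, Weeks 8, 14 and 22) = 5.
- Week 26 to end of trial: Visits 18, 22 and 27 (Weeks 32, 40 and 50) = 3.
- Patient who completes treatment: 5 + 3 = **8**.
- By method (Section 5.2.3): 1 serum at screening, and 8 − 1 = 7 urine.

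**Step 3. Count for a patient stopped at Week 14 for not reaching PASI50.** Section 3.1 still gives her the End-of-Treatment visit. She misses Weeks 22, 32 and 40: 8 − 3 = **5** (1 serum, 4 urine). This treats the Week 14 and End-of-Treatment tests as separate; if the visits coincide, the count is 5 − 1 = 4. The Synopsis assumes about 80% reach PASI50, so about 100% − 80% = 20% of entered patients would follow this path.

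**Step 4. Count if she is not of childbearing potential.** The Flow Chart row, the Section 4.2.2.3 rule and the Table 5.2.3: 1 entries do not apply to her: **0** tests under those rules.

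**Result:** up to 8 against 0 for the same woman, depending only on which definition the site follows.

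**The case against.** The strongest reply is that zero arises only if Section 5.2 is set aside, since its general wording would have every female tested. That is why the contrast is confined to the rules that name a population. Section 5.2 contains no definition, and Section 5 sends the reader to the Flow Chart for the schedule, where the row is restricted. It does not resolve the conflict.

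A second reply is that footnote 2 is the natural working rule: it is explicit and emphatic, and listing surgical sterilisation as acceptable birth control for women of childbearing potential fits it. This is a fair reading and supports choosing footnote 2 in the correction. It remains an inference, and the definition in Section 4.2.2.3 itself points the other way.

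Three smaller points stand:

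- The early-stopper count could be 4 rather than 5, and it says nothing about how many women are affected.
- Table 5.2.3: 1 describes urine testing from randomisation onward, whereas the Flow Chart also marks baseline and Week 8. The 8 follows the Flow Chart, to which Section 4.2.2.3 defers.
- The sterilisation bullet is a list of examples, so deleting one entry does not itself state that ligation is excluded. A cross-reference does.

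The practical consequence is also small. Pregnancy remains an exclusion (criterion 9), a reason to withdraw from treatment (Section 3.3.4.1) and reportable within 24 hours (Section 5.2.6.2).

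**Conclusion.** The contradiction is real and the Protocol is wrong as written on this point. For a premenopausal woman sterilised only by tubal ligation, the rules limited to childbearing potential require up to 8 scheduled tests under footnote 2 and none under Section 4.2.2.3.

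This rests on ligation being a form of occlusion, on following the Flow Chart schedule, and, for the full 8, on her completing treatment. The number of such women is not given and is probably small.

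The safety effect is minor and the pharmacokinetic analysis is unaffected. This is a desirable wording correction, not a threat to the trial's conclusions.

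**What to change.** Keep one definition, and let the stricter one govern pregnancy testing. Either remove tubal occlusion from the sterilisation bullet in Section 4.2.2.3 or replace that definition with a reference to footnote 2 of Section 3.3.2. The cross-reference is cleaner because it also carries over the explicit statement on ligation. The Flow Chart row needs no edit, since it carries no definition.

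Section 4.2.2.4, on male participants' partners, cites neither definition. If the stricter one is to apply to partners as well, add female surgical sterilisation to the accepted partner methods there, as Section 4.2.2.3 already does for female participants. Otherwise leave it alone.

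The cost is one line of text, possibly one added method, and up to 8 additional scheduled tests per affected woman at visits she already attends.

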4.2.2.4 Restrictions regarding male participants of reproductive potential

Male participants with female partner(s) of child-bearing potential must agree to use a medically acceptable method of contraception during the trial described in the patient information and for 6 months after the last dose of trial drug. Males should use a condom. Female partners must additionally use 1 of the following methods if they are not pregnant: hormonal contraception, IUD, diaphragm, or cervical cap. If their partner is pregnant, males must agree to use a condom and no additional method of contraception is required for the pregnant partner. Male patients must also agree to not donate sperm during the trial and for a period of 6 months after the last dose of trial drug.

Clinical Trial Protocol

Page 38 of 105

Proprietary confidential information © 2019 Boehringer Ingelheim International GmbH or one or more of its affiliated companies

4.3 TREATMENT COMPLIANCE

Compliance will be assured by the observation of trial medication administration (see Flow Chart) by dedicated trial personnel considered qualified to perform or observe the s.c. injections.

Patients showing poor compliance as assessed by missing their allocated days for trial medication administration must be counseled on the importance of good compliance to the trial dosing regimen.

Patients who are non-compliant (for instance, who do not appear for scheduled visits or violate trial restrictions) will be removed from the trial by the Investigator after consultation with the sponsor or sponsor's representative, and the eCRF will be completed accordingly.

Page 39 of 105

Proprietary confidential information © 2019 Boehringer Ingelheim International GmbH or one or more of its affiliated companies

5. ASSESSMENTS

Please refer to the Flow Chart for the schedule of assessments for the trial.

5.1 ASSESSMENT OF EFFICACY

The following assessments will be made at the time points indicated in the Flow Chart for the purposes of calculating the PASI, sPGA, scores.

5.1.1 PASI

The PASI is an established measure of clinical efficacy for psoriasis medications (R96-3541).

The PASI is a tool which provides a numeric scoring for patients' overall psoriasis disease state, ranging from 0 to 72. It is a linear combination of percent of surface area of skin that is affected and the severity of erythema, induration, and desquamation over four body regions.

The endpoints used are based on the percent reduction from baseline, generally summarized as a dichotomous outcome based on achieving over an X% reduction (or $PASI_X$), where X is 50, 75, 90, and 100.

To calculate the PASI, the 4 main body areas are assessed: **head (h), trunk (t), upper extremities (u) and lower extremities (l)**. These correspond to 10%, 30%, 20%, and 40% of the total body area, respectively.

The area of psoriatic involvement of these four areas (Ah, At, Au, and Al) is given a numerical value: 0 = no involvement, 1 = < 10%, 2 = 10% to < 30%, 3 = 30% to < 50%, 4 = 50% to < 70%, 5 = 70% to < 90%, and 6 = 90% to 100% involvement (Table 10.2: 2).

The signs of severity, erythema (E), induration (I) and desquamation (D) of lesions are assessed using a numeric scale 0-4 where 0 is a complete lack of cutaneous involvement and 4 is the severest possible involvement; scores are made independently for each of the areas, h, t, u, and l and represent a composite score for each area. An illustration of judging erythema follows: 0 = no erythema, 1 = slight erythema, 2 = moderate erythema, 3 = severe erythema, and 4 = very severe erythema.

The PASI score is calculated according to the following formula: PASI = 0.1(Eh+Ih+Dh)Ah + 0.3(Et+It+Dt)At + 0.2(Eu+Iu+Du)Au + 0.4(El+Il+Dl)Al (Appendix 10.2, Table 10.2: 4)

5.1.2 Static Physician's Global Assessment

The sPGA is a 5-point score ranging from 0 to 4, based on the physician's assessment of the average thickness, erythema, and scaling of all psoriatic lesions. The assessment is considered "static", which refers to the patient's disease state at the time of the assessments, without comparison to any of the patient's previous disease states (dynamic), whether at baseline or at a previous visit (Appendix 10.2, Table 10.2: 1).

Page 40 of 105

Proprietary confidential information © 2019 Boehringer Ingelheim International GmbH or one or more of its affiliated companies

A lower score indicates less body coverage, with 0 being clear and 1 being almost clear.

Erythema

- (0) Normal (Post-inflammatory hyperpigmentation may be present)
- (1) Pink coloration of lesions
- (2) Light red coloration of lesions
- (3) Dull to bright red coloration of lesions
- (4) Bright to deep red coloration of lesions

Induration

- (0) None
- (1) Just detectable
- (2) Mild thickening
- (3) Clearly distinguishable to moderate thickening
- (4) Severe thickening with hard edges

Scaling

- (0) No scaling
- (1) Minimal focal scaling
- (2) Predominately fine scaling
- (3) Moderate scaling
- (4) Severe /coarse scaling covering almost all or all lesions

Scoring:

Clear 0 = 0 for all 3

Almost clear 1 = mean > 0, < 1.5

Mild 2 = mean >= 1.5, < 2.5

Moderate 3 = mean >= 2.5, < 3.5

Severe 4 = mean >= 3.5

Clinical Trial Protocol

Page 41 of 105

Proprietary confidential information © 2019 Boehringer Ingelheim International GmbH or one or more of its affiliated companies

5.2 ASSESSMENT OF SAFETY

At the Screening Visit, the medical examination will include documentation of patient information, informed consent, demographics including height and body weight, smoking and alcohol history, relevant medical history and concomitant therapy, review of inclusion and exclusion criteria, review of vital signs (blood pressure, pulse rate, temperature), 12-lead ECG, laboratory tests (including virus screening, IGRA/PPD test [where applicable], pregnancy test for females), and a physical examination.

On other visits, it will include review of vital signs, 12-lead ECG, laboratory tests, pregnancy test for females and a physical examination.

Adverse events and concomitant therapies will be assessed throughout the trial.

Whenever possible, the same person should perform the physical examination throughout the trial (i.e., for all patients at each trial site).

5.2.1 Physical examination

A physical examination will be performed at the visits indicated in the Flow Chart.

The physical examination will include assessment of general appearance, body weight, skin, head, neck, throat, lymph nodes, cardiovascular and neurological systems, thyroid gland, musculoskeletal system/limbs, respiratory tract and abdomen. Clinically relevant abnormal findings will be reported as baseline conditions or AEs.

5.2.2 Vital signs

Vital signs will be assessed at the visits indicated in the Flow Chart.

Blood pressure, respiratory rate, and pulse rate measurements should be taken following at least 5 minutes rest while the patient is in a sitting position. The patient's body temperature will also be recorded. The method of measuring body temperature (oral/aural) should be consistent at a specific trial site.

The Investigator must assess all vital signs findings and if the Investigator finds any clinically relevant abnormalities, these must be reported as AEs / SAEs as appropriate (see Section 5.2.6.2).

Page 42 of 105

Proprietary confidential information © 2019 Boehringer Ingelheim International GmbH or one or more of its affiliated companies

5.2.3 Safety laboratory parameters

The laboratory tests listed in Table 5.2.3: 1 will be analysed by a central laboratory. The central laboratory provider will also provide the materials for blood sampling. Instructions for the labelling, storage, and shipment of the samples as well as details of all blood variable units and reference ranges can be found in the Laboratory Manual.

Pregnancy testing will be performed by a central laboratory using serum at screening and local laboratory using urine at all applicable visits thereafter.

For time points of laboratory sampling, see the Flow Chart.

Laboratory results (i.e., all safety laboratory and clinical laboratory data relevant for current clinical practice) of the patients will be available to the respective Investigator (via laboratory reports) and to the sponsor (via the central laboratory website) and selected abnormal laboratory alerts will be flagged to the site and sent to sponsor in real time.

The Investigator must assess all laboratory results, evaluate any change in laboratory values, and review all clinical laboratory tests for potential clinical significance at all time points throughout the trial. The Investigator should endeavor to provide a reason for all out-of-range results deemed not clinically significant. If the Investigator determines a laboratory abnormality to be clinically significant, it will be considered an AE / SAE (see Section 5.2.6.1); however, if the laboratory value abnormality is consistent with a current diagnosis, it will be documented accordingly.

Table 5.2.3: 1 Laboratory tests

Category	Test name
Haematology	Het
	Hb
	RBC count / erythrocytes
	White blood cells / leukocytes
	Platelet count / thrombocytes
Diff. Automatic	Neutrophils (relative count)
	Lymphocytes (relative count)
Diff. Manual (if Diff Automatic is abnormal)	Neutrophils, bands (stabs)
	Neutrophils, polymorphonuclear
	Lymphocytes
Enzymes	AST (GOT)
	ALT (GPT)
	Creatine Kinase (CK)
	CK-MB, only if CK is elevated
	Gamma-Glutamyl Transferase (GGT)
Electrolytes	Calcium
	Sodium
	Potassium
	Chloride
Substrates	Glucose
	Creatinine
	Bilirubin total
	Bilirubin direct (if total is elevated)
	Bilirubin indirect (if total is elevated)

Page 43 of 105

Proprietary confidential information © 2019 Boehringer Ingelheim International GmbH or one or more of its affiliated companies

	Total protein Albumin
II. B	Cholesterol, total
Urine Pregnancy test (only for female patients of	Human Chorionic Gonadotropin in the urine
childbearing potential) at randomization and	
continued as indicated in the Flow Chart (including	
EoT)	H C Cl : C I : C
Serum Pregnancy test (only for female patients of	Human Serum Chorionic Gonadotropin
childbearing potential) at screening and if urine	
pregnancy test is positive)	
Urinalysis (dipstick)	Urine Protein
	Urine Glucose
	Urine RBC / erythrocytes
Screening for infections (only at screening)	Hepatitis B (HBsAg, anti-HBc)
	Hepatitis C (anti-HCV)
	HIV-1 and HIV-2 antibody (qualitative, where
	mandated by local authorities, at the discretion of the
	Investigator where clinically indicated)
Screening for infections (at screening, Visit 14, EOT,	TB test (IGRA: QuantiFERON® Gold
and optional retest at Unscheduled visit)	assay/T-SPOT®.TB)
	(PPD skin test at the discretion of the Investigator
	where clinically indicated) ¹

Abbreviations: ALT=alanine aminotransferase; AST=aspartate aminotransferase; CK-MB=creatine kinase-MB; EoT=End-of-Treatment; GGT=gamma-glutamyl transferase; GOT=glutamic-oxaloacetic transaminase; GPT=glutamic pyruvic transaminase; Hb=hemoglobin; HBsAg= hepatitis B surface antigen; Hct=hematocrit; HIV=human immunodeficiency virus; IGRA=interferon gamma-release assay; PPD=purified protein derivative; RBC=red blood cell; TB=tuberculosis

1 There is the trial site option to perform a PPD skin test, although this will not be provided or performed at Central Lab.

